#### Administrative and Editorial Changes

Abbreviation	-	9	SMC Safety monitoring committee	SMC Safety monitoring committee
Schedule of Assessments – Period 1	Table 1	14	Vital signs (blood pressure, pulse rate)	Vital signs (blood pressure, pulse rate, body temperature )
Schedule of Assessments – Period 2	Table 2	16	Vital signs (blood pressure, pulse rate)	Vital signs (blood pressure, pulse rate, body temperature )
Screening Examination	7.1.1	38	• Vital signs (supine blood pressure and pulse rate)	• Vital signs ( supine blood pressure and pulse rate )
End of Trial Visit	7.1.3	42	• Vital signs (supine blood pressure and pulse rate)	• Vital signs ( supine blood pressure and pulse rate )
Adverse Event	7.4.1.1	44	Investigators will reference the National Cancer Institute - Common Terminology Criteria for AEs (NCI-CTCAE), Version 4.03 (publication date: 14 June 2010), a descriptive terminology that can be used for AE reporting.	Investigators will reference the National Cancer Institute - Common Terminology Criteria for AEs (NCI-CTCAE), Version 4.03 5.0 (publication date: 44 June 2010 27 Nov 2017 ), a descriptive terminology that can be used for AE reporting.
Procedure for Reporting Serious Adverse Events	7.4.1.4	46	Additional documents may be provided by the Investigator, if available (for example, laboratory results, hospital report, autopsy report).	Additional documents may be provided by the Investigator, if available (for example, laboratory results, hospital report, and autopsy report).
Protocol Amendments and List of Changes	Appendix III	70	Appendix III - Protocol Amendments and List of Changes	Appendix III IV - Protocol Amendments and List of Changes

## **New Wording**

### **Appendix III Contraception Guidance**

#### **Definitions**

##### **Woman of Childbearing Potential**

A woman is considered fertile following menarche and until becoming post-menopausal unless permanently sterile. Permanent sterilization methods include hysterectomy, bilateral salpingectomy, and bilateral oophorectomy.

##### **Women in the following categories are not considered women of childbearing potential**

4. Premenopausal female with 1 of the following:

- Documented hysterectomy
- Documented bilateral salpingectomy
- Documented bilateral oophorectomy

Note: Documentation can come from the site personnel's: review of participant's medical records, medical examination, or medical history interview.

5. Premenarchal

6. Postmenopausal female

- Females who are postmenopausal (age-related amenorrhea  $\geq$  12 consecutive months and increased follicle-stimulating hormone [FSH]  $> 40$  mIU/mL), or who have undergone documented hysterectomy, bilateral salpingectomy, or bilateral oophorectomy. If necessary to confirm postmenopausal status, FSH will be re-tested at Screening.
- Females on hormone replacement therapy (HRT) and whose menopausal status is in doubt will be required to use one of the non-hormonal highly effective contraception methods if they wish to continue their HRT during the study. However, they must discontinue HRT to allow confirmation of postmenopausal status before study enrollment.

## Contraceptive Guidance for Women of Childbearing Potential:

Highly Effective Contraceptive Methods That Are User Dependent	
Failure rate of <1% per year when used consistently and correctly a .	

• Combined (estrogen- and progestogen-containing) hormonal contraception associated with inhibition of ovulation b

• oral

• intravaginal

• transdermal

• Progestogen-only hormonal contraception associated with inhibition of ovulation b

• oral

• injectable

	
Highly Effective Methods That Are User Independent	

• Implantable progestogen-only hormonal contraception associated with inhibition of ovulation b

• Intrauterine device (IUD)

• Intrauterine hormone-releasing system (IUS)

• bilateral tubal occlusion

 
• Vasectomized partner
 
(Bilateral vasectomy of the partner is a highly effective contraceptive method provided that the partner is the sole male sexual partner of the woman of childbearing potential and the absence of sperm has been confirmed. If not, an additional highly effective method of contraception should be used.)
	
NOTES:	

a) Typical use failure rates may differ from those when used consistently and correctly. Use should be consistent with local regulations regarding the use of contraceptive methods for participants participating in clinical studies.
 
b) Hormonal contraception may be susceptible to interaction with the study drug, which may reduce the efficacy of the contraceptive method. In this case another highly effective (not hormone based) method of contraception must be utilized during the treatment period and for at least 3 months after the last dose of study treatment

AUC _{0-t}	Area under the plasma concentration-time curve from time zero (= dosing time) to the last sampling time (t_{last}) at which the concentration is at or above the lower limit of quantification
AUC _{0-∞}	Area under the plasma concentration-time curve from time zero (= dosing time) extrapolated to infinity
AUC _{extra}	The AUC from time t_{last} extrapolated to infinity
AUC _{extra%}	The AUC from time t_{last} extrapolated to infinity given as percentage of AUC _{0-∞} . AUC _{extra%} = (extrapolated area/AUC _{0-∞}) x 100
AUC _τ	The area under the plasma concentration-time curve (AUC) over the dosing interval from $T_1 = 0$ h to $T_2 = \tau$ h
BMI	Body Mass Index
CI	Confidence Interval
CL/f	Apparent total body clearance considering the fraction of dose (f) absorbed
CL _{ss} /f	Apparent total body clearance of drug at steady state following oral administration, considering the fraction of dose (f) absorbed.
C _{max}	Maximum plasma concentration observed
C _{max,ss}	Maximum plasma concentration observed in steady state
C _{min,ss}	Minimum plasma concentration observed in steady state
CV%	Coefficient of Variation
CSR	Clinical Study Report
eCRF	Electronic Case Report Form
ECG	Electrocardiogram
GeoCV%	Geometric Coefficient of Variation
GeoMean	Geometric Mean
IAP	Integrated Analysis Plan
ICH	International Conference on Harmonization
LLOQ	Lower Limit of Quantification
MedDRA	Medical Dictionary for Regulatory Activities

NCI-CTCAE	National Cancer Institute – Common Terminology Criteria for Adverse Events
PT	Preferred Term
PK	Pharmacokinetics
SAE	Serious Adverse Event
Q1	25th Percentile
Q3	75th Percentile
QTcF	Corrected QT interval per Fridericia's formula
SEM	Standard Error of the Mean
SOC	System Organ Class
SD	Standard Deviation
SEM	Standard Error of the Mean
TEAE	Treatment Emergent Adverse Event
ULOQ	Upper Limit of Quantification

3 Modification History

Unique Identifier for Version	Date of IAP Version	Author	Changes from the Previous Version
1.0	28-AUG-2018	PI	Original document

4 Purpose of the Integrated Analysis Plan

The purpose of this IAP is to document technical and detailed specifications for the final analysis of data collected for protocol MS200095-0032. Results of the analyses described in this IAP will be included in the Clinical Study Report (CSR). Additionally, the planned analyses identified in this IAP will be included in regulatory submissions or future manuscripts. Any post-hoc, or unplanned analyses performed to provide results for inclusion in the CSR but not identified in this prospective IAP will be clearly identified in the CSR.

The IAP is based upon section 8 (Statistics) of the trial protocol and protocol amendments and is prepared in compliance with ICH E9.

5**Objectives and Endpoints**

	Objective	Endpoint	IAP section
Primary Objective	To investigate the effect of tepotinib on the primary pharmacokinetic (PK) endpoints of dabigatran following oral administration of the P-gp probe substrate dabigatran etexilate after multiple dose administration of tepotinib in healthy subjects.	PK profile of dabigatran in terms of area under the concentration-time curve (AUC) from time zero to the last sampling time (AUC_{0-t}), AUC from time zero extrapolated to infinity ($AUC_{0-\infty}$), maximum plasma concentration (C_{max}) of total dabigatran (unconjugated plus conjugated) at Day 1 of Period 1 and Day 8 of Period 2 from time zero to 72 h post-dose.	16.1.1
Secondary Objective	To investigate the PK effect of tepotinib on the secondary PK endpoints of dabigatran following oral administration of dabigatran etexilate	PK profile of total dabigatran (unconjugated plus conjugated) in terms of time of the maximum drug concentration (t_{max}), terminal half-life ($t_{1/2}$), percentage of $AUC_{0-\infty}$ obtained by extrapolation ($AUC_{extra\%}$), apparent total body clearance (CL/f), apparent volume of distribution during terminal phase ($V_{z,f}$) at Day 1 of Period 1 and Day 8 of Period 2 from time zero to 72 h post-dose.	16.1.2
	To assess the safety and tolerability of tepotinib alone and upon co-administration of dabigatran etexilate.	Occurrence of treatment emergent adverse events (TEAEs, incidence, frequency, intensity and causality), occurrence of changes in safety laboratory assessments, 12-lead electrocardiograms (ECGs) and vital signs in subjects receiving tepotinib alone and together with dabigatran etexilate assessed from Day -1 of Period 1 until the End of Trial Visit.	15
Exploratory Objective	To investigate the multiple dose PK of tepotinib and its metabolites (MSC2571109A and MSC2571107A)	PK profile of tepotinib and its metabolites MSC2571109A and MSC2571107A in terms of AUC over the dosing interval (AUC_{τ}), C_{max} at steady state ($C_{max,ss}$), minimum concentration at steady state ($C_{min,ss}$), t_{max} at steady state ($t_{max,ss}$), CL/f at steady state ($CL_{ss,f}$) (parent drug only), and $t_{1/2}$ if appropriate	16.1.3
	To explore the effect of pharmacogenetics (PGx) and variations of associated genes on the PK profile of dabigatran and/or tepotinib (if applicable; participation is optional).	Genetic variants and mutations in genes that potentially influence the PK of tepotinib and/or dabigatran.	16.2

6**Overview of Planned Analyses**

All final, planned analyses identified in the Clinical Trial Protocol and in this IAP will be performed only after the last subject has completed the last visit, i.e. end of trial visit/early termination visit with all trial data in-house, all data queries resolved, and the database locked.

An interim evaluation of the safety and tolerability as well as the PK data will be performed after the first 6 subjects have completed Period 2. The description of these analyses will not be part of this IAP.

The data presented will include:

- Treatment emergent adverse events
- Plasma concentrations of tepotinib
- PK parameters of tepotinib
- Vital signs
- ECG parameters
- Safety laboratory values

A data review meeting will be held prior to database lock. In addition, no database can be locked until this IAP has been approved.

7 Changes to the Planned Analyses in the Clinical Trial Protocol

The statistical methods as described in the protocol were adopted.

Scatter plots for the primary endpoint will show geometric means (GeoMean) instead of median, 25th Percentile and 75th Percentile (Q1 and Q3).

8 Protocol Deviations and Analysis Sets

8.1 Definition of Protocol Deviations and Analysis Sets

Important protocol deviations are protocol deviations that might significantly affect the completeness, accuracy, and/or reliability of the study data or that might significantly affect a subject's rights, safety, or well-being.

The following deviations will be identified and confirmed prior to or at the Data Review Meeting at the latest.

Important protocol deviations include

- Deviations from the inclusion and exclusion criteria
- Concomitant medication violations (see Section 6.5.1 of the protocol)
- Use of prohibited medicines (see Section 6.5.2. of the protocol)
- Subjects that receive incorrect treatment or dose
- Sample processing errors that may lead to inaccurate bioanalytical results
- Vomiting or diarrhea following oral dosing (these instances will be discussed on a case-by-case basis)

- Deviation from Good Clinical Practice
- Non-compliance to study procedures or deviations from study procedures likely to affect the primary endpoints (e.g. subject develops withdrawal criteria whilst on the study but is not withdrawn)
- Deviation from study medication compliance in terms of medical conditions and/or AEs that may have interfered with drug disposition or with respect to factors likely to affect the primary endpoints

All important protocol deviations will be documented in CDISC datasets whether identified through sites monitoring or medical review.

8.2 Definition of Analysis Sets and Subgroups

For purposes of analysis, the following populations are defined:

Population	Description
Screening	The screening analysis set will include all subjects who provided signed informed consent, regardless of treatment status in the trial. This set will be used for subject disposition.
Safety	The Safety Analysis Set will include all subjects who have received at least 1 dose of planned IMP. Subjects will be analyzed according to the actual treatment they receive.
Pharmacokinetic	The PK Analysis Set will include all subjects who have completed at least 1 period without any relevant protocol violations with respect to factors likely to affect the comparability of PK results, with adequate study medication compliance, and with evaluable dabigatran PK data. Assessment of data sufficiency will be done by the responsible pharmacokineticist before database lock, ie PK data will be available and included in the database before data base lock. Subjects may be excluded after vomiting or following diarrhea in a particular period as this could render the plasma concentration-time profile unreliable. The use of a concomitant medication that might interfere with the PK of any investigational drug could be a reason for excluding a subject.

9

General Specifications for Data Analyses

Statistical analyses will be performed using the computer program package SAS® System for Windows™ (Version 9.4 or later; SAS Institute, Cary, North Carolina, USA).

The results of this trial will be reported using summary tables, figures, and data listings, as appropriate. All data will be summarized by treatment and/or scheduled time point, as appropriate.

For demographic, baseline and safety assessments, continuous measurements will be summarized by means of descriptive statistics (ie, number and percentage of observations, number and percentage of missing observations, mean, standard deviation [SD], median, 25th and 75th percentiles [Q1 and Q3], minimum, and maximum) and categorical data will be summarized by means of frequency tables (ie, count and percentages), if not stated otherwise. Mean, Median, Q1, Q3, Min, Max will have the same precision as the SDTM data (decimal places). SD will be presented with one decimal place more than the mean. Unless otherwise stated the calculation of proportions will be based on the number of subjects at risk or with available measurements in the analysis set of interest for safety outputs. For subject disposition and demographic tables the denominator will be the number of subjects in the analysis set. Counts of missing observations will be included as a separate category.

If not otherwise specified, 'baseline' refers to the last scheduled measurement before administration of the first drug in each period. However, if a subject is missing the baseline collection, the previous non-missing evaluation could become the baseline value (e.g. from screening/admission). If no baseline or previous to baseline evaluations exist then the baseline value will be treated as missing.

The following calculations and derivations, as applicable, will be used:

- Change from baseline: post-baseline visit value - baseline value
- Duration of AE (in days hh:mm) = end date and time - start date and time of the AE, if missing time for either the beginning or end then = end date – start date + 1
- Days hh:mm from dosing = start date and time of the event - date and time dose administration; (for treatment- emergent AEs), if missing time for either the beginning or end then = end date – start date + 1
- Rel. Day in study of AE = start date of the event – date of First Admin + 1 (for AEs on or after the day of dosing)
- Rel. Day in study of AE = start date of the event – date of First Admin (for AEs before the day of dosing)

Repeated laboratory assessments will be flagged as repeats in the subject data listings and not included in summary tables statistics (unless the scheduled measurement was considered unreliable, e.g. due to technical reasons, and needed to be replaced by an unscheduled repeat measurement).

In this phase 1 PK study missing observations will be assumed to be missing completely at random (MCAR). No action will be taken to handle missing data. A subject who withdraws prior

to the last planned observation in a trial period will be included in the analyses up to the time of discontinuation.

The following treatmentlabels will be used in listing and tables:

- dabigatran
- dabigatran + tepotinib

10 Trial Subjects

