### **4.2 Secondary Objectives**

- To investigate the PK effect of tepotinib on the secondary PK endpoints of dabigatran following oral administration of dabigatran etexilate
- To assess the safety and tolerability of tepotinib alone and upon co-administration of dabigatran etexilate.

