## **6.2 Dosage and Administration**

Subjects will receive the following 2 treatments:

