### **Treatment B (Period 2): Tepotinib and Dabigatran Etexilate**

On Days 1 to 7 of Period 2, 500 mg tepotinib will be administered together with 240 mL of water after a standard breakfast (about 30 min after start of breakfast). A standardized breakfast must be consumed completely within 25 min.

On Day 8 of Period 2, a single dose of 75 mg dabigatran etexilate and 500 mg tepotinib will be administered concomitantly in a fed state with 240 mL water. A standardized breakfast will be administered 30 min prior to tepotinib and dabigatran etexilate dosing and must be consumed completely within 25 min. 30 min after start of the breakfast, 500 mg tepotinib and 75 mg dabigatran etexilate will be administered together with 240 mL of water.

The minimum washout period after administration of dabigatran etexilate as mesilate in Period 1 is at least 72 h (Day 4) from dosing on Day 1 of Period 1 to prevent PK carryover effects between periods. Considering that in Period 2 dabigatran etexilate will be administered on Day 8 (= 168 h) of Period 2, the resulting interval between the 2 administrations of dabigatran etexilate will be 240 h (= 72 h [Day 1 to Day 4 of Period 1] + 168 h [Day 1 to Day 8 of Period 2]) or 10 days.

On Days 7 and 8 of Period 2, subjects will stay in a semi-recumbent position for 4 h post-dose, except for use of the toilet, when the subjects will be allowed to leave the bed without undue physical stress/activity.

Standardized meals will be served 4 h (lunch), 8 h (snack) and 10 h (dinner) after dosing on Days 7 and 8; other meals will be served at customary times during the inpatient period.

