11.3 Other Baseline Characteristics

Other baseline characteristics will be listed by subject and summarized using the following information from the Screening/Baseline Visit eCRF pages.

Other baseline characteristics:

- Smoking status
- Alcohol consumption

12 Previous or Concomitant Medications/Procedures

Previous medications are medications, other than trial medications and pre-medications for trial drug, which started and stopped before first administration of trial drug.

Concomitant treatments are medications, other than trial medications, which are taken by subjects any time on-trial (on or after the first day of trial drug treatment for each subject).

In case the date values will not allow to unequivocally allocating a medication to previous or concomitant medication the medication will be considered as concomitant medication

Any previous and concomitant medication will be encoded with WHO-DD, latest version. Prior and concomitant medications will be listed by subject (all subjects).

The following information will be displayed in a listing: generic or trade name (as reported in eCRF), WHO drug name (including ATC-2nd level and preferred term), dose/unit, route, frequency, reason for use, start/end date and time.

Concomitant procedures will be presented in a data listing.

13

Treatment Compliance and Exposure

A listing of date and time of each drug administration and each blood sampling including time deviations will be provided sorted by subject.

14

Efficacy Analyses

Not applicable.

15

Safety Analyses

The subsections in this section include specifications for summarizing safety endpoints that are common across clinical trials such as adverse events, laboratory tests and vital signs.

Safety data analysis will be conducted on the Safety Analysis Set.

15.1

Adverse Events

The number and percentage of subjects experiencing at least one TEAE will be summarized by treatment as well as the number of events. A TEAE is an AE with onset after start of treatment. Tables by relationship to trial drug and by severity will be generated. AEs will be coded using Medical Dictionary for Regulatory Activities terminology, latest version.

Incomplete TEAE-related dates will be handled as follows:

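### SAP 9 has only two treatment labels, so seven days of tepotinib alone are pooled with co-administration in the by-treatment TEAE, QTcF-category and ECG-interpretation tables

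*SAP*

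**What the plan says.** - **Objective.** Protocol 4.2 sets the secondary safety objective: "To assess the safety and tolerability of tepotinib alone and upon co-administration of dabigatran etexilate". SAP 5 words the endpoint as TEAEs and changes in laboratory values, ECGs and vital signs "in subjects receiving tepotinib alone and together with dabigatran etexilate assessed from Day -1 of Period 1" to the End of Trial Visit, and refers it to SAP 15.
- **Treatments.** Protocol 6.2 says "Subjects will receive the following 2 treatments". The first is dabigatran etexilate alone in Period 1. The second is headed "Treatment B (Period 2): Tepotinib and Dabigatran Etexilate" and covers the tepotinib-only Days 1-7 as well as Day 8, when both drugs are given.
- **Labels.** SAP 9: "The following treatmentlabels will be used in listing and tables", followed by 'dabigatran' and 'dabigatran + tepotinib' only.
- **Timing of events.** SAP 15.1: "A TEAE is an AE with onset after start of treatment". SAP 9 derives "Days hh:mm from dosing = start date and time of the event - date and time dose administration" without naming the dose from which time is counted.
- **Tables.** SAP 15.1 and 15.2 summarise TEAEs, discontinuations due to TEAEs and SAEs by treatment. SAP 15.5 tabulates QTcF categories over any post-dose assessment by treatment group, and ECG interpretation by treatment; neither has a day or visit split. In contrast, SAP 15.3 summarises laboratory values over time and SAP 15.4 summarises vital signs by visit.

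**The concern.** The two labels suit the dabigatran PK comparison, which sets Period 1 Day 1 against Period 2 Day 8. They do not suit the safety objective: one of the two conditions it names, tepotinib alone, has no label of its own, while dabigatran alone, which it does not name, has one.

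Protocol 5.2.3 notes that multiple doses of tepotinib have not been given to healthy subjects before. A reader of the three sets of tables would want to know whether an event or a QTcF outlier arose during those first seven days or after dabigatran was added. A column headed 'dabigatran + tepotinib' that includes the seven days would not show this, and its heading would misdescribe part of its content. A split made later would count as unplanned, and SAP 4 requires such analyses to be identified as unplanned in the study report.

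**Working it through.** There is no planned figure to reproduce. The check has two parts: which column the Day 1-7 data enter, and how much of that column they make up.

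**Which column.** SAP 9 offers two labels. Protocol 6.2 offers two treatments, and these map one to one onto the labels, with all of Period 2 as the second. The TEAE definition separates only before and after the start of treatment. The time-from-dosing derivation names no dose. SAP 8.2 analyses subjects by the treatment they actually receive, but adds no label and no time window. Protocol 8.4 and 8.5.4 add neither. So Days 1-7 go under 'dabigatran + tepotinib'. If that mapping is refused, they have no column. Neither reading gives a tepotinib-alone column.

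**Time at risk in Period 2.** Inputs: Day 8 dosing is 168 h after Day 1 dosing (Protocol 5.1 and 6.2); End of Trial is 7 ± 1 days after the last dose, so 6 × 24 = 144 h to 8 × 24 = 192 h (Protocol Table 2, footnote a). Share before the Day 8 dose:

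- End of Trial at 8 days: 168 / (168 + 192) = 46.7%
- End of Trial at 6 days: 168 / (168 + 144) = 53.8%

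**Scheduled ECGs** (Protocol Table 2, footnote d). Before the Day 8 dose: 7 at 6 h on Days 1-7; 6 pre-dose on Days 2-7; 1 pre-dose on Day 8. The Day 1 pre-dose ECG precedes tepotinib and is not counted. After the Day 8 dose: 4, 8, 24, 48 and 72 h = 5, or 6 with End of Trial.

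| ECGs counted as post-dose | With End of Trial | Without |
|---|---|---|
| Days 1-7: 6 h only | 7/(7+6) = 53.8% | 7/(7+5) = 58.3% |
| Also pre-dose, Days 2-8 | 14/(14+6) = 70.0% | 14/(14+5) = 73.7% |

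The range of 54-74% arises because SAP 15.5 does not say whether a pre-dose ECG on a later dosing day counts as post-dose.

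**Tepotinib PK tables.** SAP 16.1.4 also tabulates tepotinib concentrations by treatment. Samples (Protocol Appendix II): Day 6 pre-dose 1 + Day 7 pre-dose 1 + five from 15 to 90 min + seven from 2 to 24 h = 14. The 24 h sample is taken before Day 8 dosing, so all 14 precede co-administration. Only the column heading is wrong here; nothing is pooled.

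**Laboratory shift (secondary point).** SAP 15.3 plans a within-period shift from pre-dose tepotinib to discharge. Pre-dose samples exist on Days 1, 2, 7 and 8, so taking Day 1 as the start is an inference. Discharge is Day 11. On that reading the shift spans both phases. Coagulation is tabulated with hematology but sampled in Period 2 only at Day 1 pre-dose, Day 8 pre-dose, Day 8 4 h and Day 9 24 h (Table 2, footnote i), so its shift has no end value.

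**The case against.** The strongest reply is that little is lost. The labels follow the protocol's own treatment definitions. Laboratory summaries over time and vital signs by visit already keep Days 1-7 apart. The listings give AE timing, dosing times and ECG time points, and with 20 subjects the split can be rebuilt by hand. SAP 15.5 also plans descriptive statistics for ECG intervals. It says only by treatment, but SAP 9 allows summaries by scheduled time point; if that is done, the maximum QTcF on each day would be visible. Safety and PK data are reviewed separately after the first 6 subjects. The percentages above count hours and ECGs, whereas the tables count subjects.

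All of this stands as a limit on importance, but none of it creates a tepotinib-alone column. The 6-subject review is outside the SAP's analyses by its own statement in SAP 6. The rows for events related to tepotinib or to dabigatran record the investigator's causality judgement, not what had been given at onset.

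Two stronger readings are tempting. A reader might infer that Days 1-7 carry no label at all and drop out of the tables. Protocol 6.2 points the other way: the label is too coarse, not absent. A reader might also infer that half of the secondary safety objective has no planned table. That goes too far, because laboratory values and vital signs are covered; the gap is in the TEAE and ECG-category parts.

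**Conclusion.** The point holds and should be fixed in the SAP. Followed as written, the plan puts seven of the eight tepotinib doses under a label that names dabigatran before any Period 2 dabigatran is given. It does so in the TEAE tables (including SAEs and discontinuations), the QTcF-category table and the ECG-interpretation table. About half of Period 2 time at risk (47-54%) and 54-74% of the pooled ECGs come before the Day 8 dose. These shares assume a subject who completes the schedule, and they do not predict how many events or subjects would move between columns.

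The conclusion rests on reading the two labels as the protocol's two treatments; the literal alternative leaves the same gap. The analyses concerned are descriptive, and no primary PK result changes. The laboratory-shift point depends on reading the shift as Day 1 to Day 11.

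**What to change.** In SAP 9, use three labels:

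- 'dabigatran': Period 1 dose to before the first tepotinib dose
- 'tepotinib': first tepotinib dose to before the Day 8 dose
- 'dabigatran + tepotinib': Day 8 dose to End of Trial

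Then state the following.

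1. TEAEs are assigned by onset date and time; a Day 8 onset with missing time goes to the combination.
2. ECGs are assigned by assessment time. An ECG after the first dose of a phase and before the first dose of the next counts as post-dose for that phase, so the Day 8 pre-dose ECG belongs to 'tepotinib'. By the same rule the Period 2 Day 1 pre-dose ECG falls in 'dabigatran' while also being the Period 2 baseline; say so.
3. Change from baseline keeps the existing per-period baseline.
4. The denominator stays as SAP 9 has it: "the calculation of proportions will be based on the number of subjects at risk or with available measurements".
5. Any TEAE with an imputed onset date is footnoted as of uncertain phase. SAP 15.1 may move it to the start of trial treatment, to an earlier resolution date, or to the first of a month. The last can stay inside Period 2: if Period 2 Day 1 were 28 March, an April onset with the day missing would become 1 April, which is Day 5.
6. Tepotinib PK tables carry the 'tepotinib' heading.
7. Laboratory shifts: add Day 1 pre-dose to Day 8 pre-dose for tepotinib alone. For coagulation, name end points from samples already planned: Day 8 pre-dose for tepotinib alone, Day 8 4 h and Day 9 24 h after co-administration.

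The cost is SAP wording, one extra column in the affected tables and one or two extra shift tables; there are no new visits or samples. The drawbacks are that late-onset tepotinib events after the Day 8 dose count under the combination and that each phase is shorter. Because the sequence is fixed, the columns show timing and not the causal effect of adding dabigatran.
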